6.7 TREATMENT AFTER THE END OF THE STUDY

Currently, the Sponsor does not have any plans to provide RO7121661 or any other study treatments or interventions to the participants after the end of the study or when participants discontinue or have been withdrawn from the study. The Sponsor will evaluate whether to continue providing RO7121661 to participants after the main study is over, in accordance with the Roche Global Policy on Continued Access to Investigational Medicinal Product, available at the following website:

http://www.roche.com/policy continued access to investigational medicines.pdf

7. DISCONTINUATION OF STUDY TREATMENT AND PARTICIPANT DISCONTINUATION/WITHDRAWAL

An excessive rate of withdrawals (either participants discontinuing study treatment or withdrawing from the study) can render the study non-interpretable. Therefore, unnecessary withdrawal of participants should be avoided and efforts should be taken to motivate participants to comply with all the study specific procedures as outlined in this protocol.

Details on study and site closures are provided in Appendix 1 Study Governance Considerations Study.

7.1 DISCONTINUATION OF STUDY TREATMENT

See the SoA (Section 1.3) for data to be collected at the time of treatment discontinuation and follow-up and for any further evaluations that need to be completed.

Participants must permanently discontinue study treatment if they experience any of the following (also see Appendix 6):

- Intolerable toxicity related to study treatment, including development of an immune mediated adverse event determined by the Investigator to be unacceptable given the individual participant's potential response to therapy and severity of the event
- Pregnancy.
- Grade 4 IRR.
- IgE-mediated hypersensitivity reactions, including anaphylaxis.
- Any toxicity which is not manageable with dose delays (as allowed per protocol), dose decrease, and appropriate treatment.
- Unacceptable toxicity as determined by Investigator.

- For cardiac changes:
 - If a clinically significant finding is identified (including, but not limited to QTcF≥500 ms and/or an increase of≥60 ms in QTcF from screening), the Investigator or qualified designee will determine if the participant can continue in the study and if any change in clinical management is needed. This review of the ECG printed at the time of collection must be documented. Any new clinically relevant finding should be reported as an AE.
- Any medical condition that the Investigator or Sponsor determines may jeopardize the participant's safety if he or she continues in the study.
- Investigator or Sponsor determines it is in the best interest of the participant.
- Participant non-compliance, specifically defined as disregarding protocol.
- Symptomatic disease progression when there is a consensus that the participant will not benefit from study treatment.

As with other immunotherapies, treatment beyond RECIST Version 1.1 progression may be considered following discussion between the Investigator and the Sponsor. When considering treatment beyond progression, locally approved and available treatment options need to be taken into account.

The criteria below are needed for continuing treatment beyond initial apparent progressive disease per RECIST Version 1.1 (e.g., radiological progression secondary to tumor inflammation):

- Absence of clinically important symptoms and signs (including worsening of laboratory values) indicative of disease progression
- Investigator-assessed potential clinical benefit for the participant
- The participant is tolerating study drugs.
- No decline in ECOG performance status.
- Absence of rapid progression of disease or of progressive tumor at critical anatomical sites (e.g., cord compression) requiring urgent alternative medical intervention.

Participants who discontinue study treatment will be asked to return to the clinic for an End-of-Treatment visit (see Section 8.10.3) and may undergo follow-up assessments (see Section 8.10.4). The primary reason for study treatment discontinuation should be documented on the appropriate eCRF.

Participants who discontinue study treatment prematurely may be replaced for the following reasons to ensure adequate numbers of evaluable participants:

 Participant who withdraws from the study prior to the treatment start may be replaced and will not be entered into the database.

- Participants who fail to complete their DLT assessment period because of non-drugrelated reasons.
- In the case of a major protocol violation participants will be excluded from the MTD/DLT analysis but might continue the treatment if deemed beneficial, and if there is no safety concern associated with the protocol violation criteria and according to clinical judgment.

Participants will be treated until disease progression, loss of clinical benefit, unacceptable toxicities, or withdrawal from treatment for other reasons, or death.

7.1.1 Temporary Interruption

Before permanently discontinuing study treatment (regardless of whether initiated by the participant, the Investigator or Sponsor), an interruption should be considered. Participants, who have temporarily interrupted study treatment, should be considered to re start as soon as medically justified in the opinion of the Investigator.

Dose interruptions for reason(s) other than toxicity, such as surgical procedures, may be allowed. The acceptable length of interruption will depend on the *discussion* between the Investigator and the Medical Monitor.

In case of toxicity requiring RO7121661 treatment to be put on hold, the study treatment should only re-start once the toxicities have resolved to NCI CTCAE Grade ≤ 2 for hematological toxicities or Grade ≤ 1 for non-hematological toxicities. Participants who do not recover from drug-related toxicities after omission of up to 2 doses (delay of 4 weeks in the Q2W schedule) of RO7121661 and who in the opinion of the Investigator are not receiving clinical benefit from RO7121661 treatment, should be permanently discontinued from the study.

If in the judgment of the Investigator, the participant is likely to derive clinical benefit from RO7121661 after a hold of more than 2 doses, study drug may be re-started.

If an IRR develops, the infusion of RO7121161 should be slowed down or interrupted. The participant should be monitored until complete resolution of the symptoms and treated as clinically indicated. Treatment or concomitant medication may include acetaminophen/paracetamol, antihistamine, IV saline, oxygen, bronchodilators, corticosteroids, and vasopressors, depending on the symptoms (see Section 8.3.8). Study treatment should be re-started as soon as medically justified in the opinion of the Investigator.

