4.1.1 Length of the Study

The duration of the study for each participant will be up to 27 months (Parts A and B), divided as follows:

- Screening: Days 28 to 1
- Treatment Period: Cycle 1 Day 1 to Month 24 (may be modified if supported by emerging data).
- Safety follow-up: 60 (\pm 7) days after last treatment with RO7121661 for Part A; 90 (\pm 7) days after last treatment with RO7121661 for Part B.
- Survival follow-up: 90 (\pm 7) days after last treatment with RO7121661; then every 3 months (\pm 2 weeks) for total 24-month period after initial dose.

The treatment period may be prolonged past month 24 if the participant is still benefitting from treatment at the time of the last visit at the end of the two-year period. Participants may extend treatment within the ongoing study whether they are on treatment or are on a treatment pause at the 24-month time point. During the extended treatment period, the participant follows the SoA as indicated for "Subsequent Cycles." Participants will be treated until disease progression, unacceptable toxicities, or

withdrawal of consent. For participants who extend their treatment, the safety follow-up will be performed 60 (\pm 7) days for Part A or 90 (\pm 7) days for Part B after the last treatment with RO7121661 and survival follow-up every 3 months (\pm 2 weeks) thereafter for a total of 48 months after initial dose, or end of the study.

4.1.2 Dose-Escalation Decision Criteria

For Part A, RO7121661 dose-escalation will be carried out according to a mCRM with EWOC design and will be based on the occurrence of DLTs. The dose-toxicity relationship is described by a 2-parameter logistic regression model, where the probability of DLT is expressed as a function of dose. The model is continuously updated as additional participant information becomes available (for further information see Appendix 10).

A minimum of participants per cohort will be enrolled and treated in a sequential manner with one week between the first and second participant and at least 2 days between subsequent participants. However, if the first participant experiences a DLT within the first week, then the time between the treatment of subsequent participants within the same cohort may be increased.

A new cohort can be opened when at least participants per cohort are considered DLT evaluable, i.e., if they received 2 doses and either:

- experienced a DLT within the DLT period
- cleared the DLT period without a DLT

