6.5.1 Permitted Therapy

Any medication or vaccine (including over-the-counter [OTC] or prescription medicines, approved dietary and herbal supplements, nutritional supplements) used by a participant during screening until the follow-up visit must be recorded along with reason for use, dates of administration (including start and end dates) and dosage information (including dose and frequency). The Medical Monitor *can advise* if there are any questions regarding concomitant or prior therapy.

All concomitant medications *or vaccines* should be reported to the Investigator and recorded on the Concomitant Medications electronic Case Report Form (eCRF). All therapy and/or medication administered to manage adverse events should be recorded on the Adverse Event eCRF.

Radiotherapy

Participants should not receive study treatment during radiation treatment.

The use of limited field palliative radiotherapy is allowed at any time during the study, **except for:**

- Days where RO7121661 is administered.
- During the DLT evaluation window.
 - If radiotherapy is administered during the DLT evaluation window, the participant will not be evaluable.

6.5.2 Prohibited Therapy

All medications (prescription and OTC) taken within 30 days of study screening will be recorded on the appropriate eCRF. As a general rule, no concomitant medication will be permitted, with the exception of medications to treat AEs and therapy for pre-existing conditions, unless the rationale for exception is discussed and clearly documented.

Use of the following therapies is prohibited during the study and for at least 28 days or 5 half-lives of the drug, whichever is shorter, prior to initiation of study treatment, unless otherwise specified below:

- Investigational or unlicensed/unapproved agents
- Immunotherapy/radio-immunotherapy
- Chemotherapy / targeted therapy
- Radiotherapy (with the exception of limited field palliative radiotherapy).
- Biologic agents (e.g., bevacizumab, cetuximab).
- Chronic use of steroids (inhaled and topical steroids are permitted) at baseline of >10 mg of prednisone/day or equivalent. Concurrent high doses of systemic corticosteroids will not be allowed.
- Administration of a live, attenuated vaccine within 28 days before Cycle 1 Day 1 or anticipation that such a live attenuated vaccine will be required during the study.

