9.3 POPULATIONS FOR ANALYSES

For purposes of analysis, the following populations are defined in Table 7.

Table 7 Analysis Populations

Population	Description
Dose Limiting Toxicity	The DLT-evaluable population is defined as all participants who received at least two doses of study medication and either:
	experienced a DLT within the DLT period OR
	cleared the DLT period without a DLT
	The DLT period is 21 (Q2W) from Day 1/Cycle 1 to Day 7/Cycle 2. If there is a delay in Cycle 2 treatment the DLT period should be adjusted to cover Day 7/Cycle 2 up to a maximum of 35 (Q2W) days, since the maximum dose delay allowed is 14 days.
Efficacy	All participants in the safety population who received at least one dose of study drug and who have at least one baseline and one on-study tumor assessment. Participants who received at least one dose of study drug and discontinued the study because of progression before the first on-study tumor assessment will be considered as response-evaluable.
Safety	All participants who received at least one dose of the study treatment, whether prematurely withdrawn from the study or not, will be included in the safety analysis. Unless otherwise specified, the safety population will be the default analysis set used for all analyses.
Pharmacokinetic	All participants who have received at least one dose of study treatment and who have data from at least one post-dose sample will be included in the PK analysis population. Participants will be excluded from the PK analysis population if they significantly violate the inclusion or exclusion criteria, deviate significantly from the protocol, or if data are unavailable or incomplete which may influence the PK analysis. Excluded cases will be documented together with the reason for exclusion. All decisions on exclusions from the analysis will be made prior to database closure.

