PFS will be defined as the time from study treatment initiation (Cycle 1 Day 1) to the first occurrence of documented disease progression (based on RECIST Version 1.1 Investigator's assessment) or death from any cause, whichever occurs first. For

participants who do not have documented progressive disease or death during the study, PFS will be censored at the day of the last tumor assessment.

Sensitivity analyses of response endpoints (ORR, DRC, DoR, and PFS) may include the evaluation of response according to iRECIST.

OS is defined as the time from the first dose of study treatment to the time of death from any cause. Participants who are still alive at the time of analysis will be censored at the time of their last study assessment (for active participants) or at the last date known alive (for participants in follow-up).

9.4.3 Safety Analyses

Unless otherwise specified all safety analyses listed in Table 9 will be based on the safety population. All safety parameters will be analyzed using descriptive statistics, summarized and presented in tables. Data will be summarized by dose and regimen (if applicable) within each part.

Safety will be assessed through summaries of DLTs (for Part A), adverse events, changes in laboratory test results, changes in vital signs and ECGs, and exposure to study treatment.

Table 9 Safety Statistical Analysis Methods

Endpoint	Statistical Analysis Methods
AEs	The original terms recorded on the eCRF by the Investigator for AEs will be coded by the Sponsor.
	For classification purposes, preferred terms will be assigned by the Sponsor to the original terms entered on the eCRF, using the most up-to-date version of the MedDRA terminology for AEs and diseases. AEs will be graded according to NCI CTCAE grades v5.0.
	Adverse events will be summarized by mapped term and appropriate thesaurus level. Toxicity grade, seriousness, and relationship to study treatment will be presented, as well as summaries of deaths, AEs leading to death and premature withdrawal from study treatment. Glossary of AEs, medication, and procedures will be provided.
Nature and frequency of DLTs	DLT events will be presented by individual listings. The MTD will be estimated with a mCRM–EWOC using DLT-evaluable participants. The MTD estimate will be presented along with 90% Credible Intervals.

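### Sections 7.1 and 6.5.1 exclude major violators and irradiated participants from the DLT analysis even after a DLT, whereas Section 4.1.2 and Table 7 count them

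*Combined protocol and SAP*

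**What the plan says.** Two passages remove participants from the DLT analysis.

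- Section 7.1, among the reasons for replacement: "In the case of a major protocol violation participants will be excluded from the MTD/DLT analysis but might continue the treatment if deemed beneficial".
- Section 6.5.1 (repeated in the synopsis): "If radiotherapy is administered during the DLT evaluation window, the participant will not be evaluable".

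Three passages define or use the DLT-evaluable set without either exclusion.

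- Section 4.1.2 opens a new cohort once enough participants "are considered DLT evaluable, i.e., if they received 2 doses and either" had a DLT in the window or cleared it.
- Section 9.3, Table 7: "The DLT-evaluable population is defined as all participants who received at least two doses of study medication and either" of two conditions holds, the first being "experienced a DLT within the DLT period OR" clearance of the window without one.
- Section 9.4.3, Table 9, estimates the MTD by the mCRM-EWOC model "using DLT-evaluable participants" and reports it with a 90% credible interval.

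Table 7 does write out a violation rule for another population: "Participants will be excluded from the PK analysis population if they significantly violate the inclusion or exclusion criteria, deviate significantly from the protocol". It adds that such PK exclusions are documented and settled before database closure. The DLT row has no counterpart. The documents do not define a major protocol violation, and they do not say who decides this exclusion or when.

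**The concern.** Take a participant who received two doses, had a DLT in the window and also had a major violation or radiotherapy in the window. Table 7 includes this participant in the set on which the MTD is estimated; Section 7.1 or 6.5.1 takes the same participant out. The plan does not say which passage governs.

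Under the excluding passages, the model loses an event that Section 4.1.3 has already required to be related to study drug and not due to disease progression or another clearly identifiable cause. The exclusion is therefore not needed to screen out events caused by something else. With few DLTs in an escalation, the loss of one can move the model output in the less cautious direction. The study is open-label, and nothing fixes the classification before the DLT status is known.

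**Working it through.** **The passages applied to one case** (two doses, DLT in the window, major violation)

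- Section 4.1.2: evaluable.
- Table 7: in the DLT-evaluable population.
- Table 9: therefore in the MTD estimate.
- Section 7.1: excluded from the MTD/DLT analysis, with no condition on outcome.

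Radiotherapy in the window gives the same conflict with Section 6.5.1 in place of Section 7.1.

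**Size from the printed mock runs** (Appendix 10 Table 1: cohorts of three, no DLT in earlier cohorts)

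- 210 mg, 0 versus 1 DLT: 615 versus 220 mg; 615/220 = 2.8.
- 1840 mg, 0 versus 1 DLT: 2100 versus 2050 mg; 2100/2050 = 1.02.
- The small effect at 1840 mg holds for a first DLT only. For 1 versus 2 DLTs that row prints 2050 versus 550 mg; 2050/550 = 3.7.

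**Rebuilding the model.** The printed rows compare outcomes in a full cohort of three. An exclusion without replacement leaves two, so the Appendix 10 model was rebuilt:

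- logit p(d) = α + β ln(d/70).
- (α, β) bivariate normal, mean (−1.736, 0.326), variances 0.8948 and 0.0747, covariance 0.1859.
- Recommendation = the grid dose that maximises P(0.20 ≤ p ≤ 0.35), subject to P(p > 0.35) < 0.25 and the stated increment caps.

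For the 210 mg row with 0, 1, 2 or 3 DLTs this gives 630 / 220 / 82.5 / 45 mg against the printed 615 / 220 / 82.5 / 45 mg, all within 3% (630/615 = 1.02). Other rows fit less closely where the maximum is flat (for example about 640 against 550 mg), so only the 210 mg row is used below.

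| Data at 210 mg (0/3 earlier at 70 mg) | Model output | P(DLT rate > 35% at 210 mg) | Posterior mean DLT rate |
|---|---|---|---|
| DLT participant kept, 1/3 | 220 mg | 0.165 | 22% |
| DLT participant dropped, 0/2 | 630 mg | 0.053 | 14% |
| Dropped and replaced by a participant without a DLT, 0/3 | 630 mg | 0.035 | 13% |
| Violator without a DLT dropped, 1/2 | 155 mg | 0.232 | 25% |

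Rows 2 and 3 against row 1 show the less cautious shift (630/220 = 2.9). Row 4 against row 1 shows the opposite shift when the excluded violator had no DLT. These are model outputs used to size the effect, not dose proposals.

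**The case against.** Much can be said for the plan.

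- **The rule works in both directions.** It removes any major violator. Without a DLT, removal raises the estimated rate (1/3 becomes 1/2). A reader might infer that it can only delete DLTs; the text does not support that. This stands.
- **The event is not lost to the study.** Table 7 says of the safety population: "All participants who received at least one dose of the study treatment, whether prematurely withdrawn from the study or not, will be included". DLTs are listed individually (Table 9) and notified promptly to the sponsor (Section 4.1.5). Dose decisions use all relevant data, and the model sets only an upper limit (Sections 4.1.5 and 4.3). This stands, but it does not repair the MTD estimate itself.
- **The clause may not be aimed at DLT cases.** Section 6.6 has participants with a DLT discontinue, subject to a dose-reduction option, whereas this clause speaks of violators who may continue if there is no safety concern. Section 7.2 says that safety withdrawals are not replaced. That makes the narrower reading plausible and limits replacement. It does not limit exclusion from the analysis, and the clause does not state the narrower reading.
- **The scattered criteria may be meant as supplements to Table 7.** That is possible, but Table 7 spells out a violation rule for PK and none for DLT, so a programmer working from Table 7 would not apply one.
- **Escalation is over.** Sections 4.4 and 4.3 give 2.1 g Q2W as already selected for Part B. This stands and narrows what is at stake.

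**Conclusion.** The passages conflict, and the conflict should be removed, but this is a low-priority point. When applied to a participant with a DLT, the exclusion is anti-conservative for the model: 615 versus 220 mg in the 210 mg mock run, and only 2100 versus 2050 mg for a first DLT at 1840 mg. When applied to a violator without a DLT, it errs the other way.

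Three stronger conclusions might be inferred and are not supported. First, one exclusion does not generally decide the result; the effect depends on the dose row and the number of DLTs. Second, nothing shows that Part A's toxicity signal was reduced: the documents report one DLT, at 1.2 g, no MTD, and no participant excluded under these rules. Third, the documents do not say that exclusions are decided after the outcome is known; they give no timing at all, which is a gap rather than a stated practice.

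With the Part B dose selected, the remaining exposure is mainly the reported MTD estimate, its 90% credible interval and any further model update. The sizes rest on cohorts of three with no earlier DLT, as in the mock runs, and on reading the exclusions as unconditional, as they are written.

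**What to change.** - Put one DLT-evaluable definition in Sections 4.1.2, 6.5.1, 7.1 and Table 7, and define a major protocol violation.
- Limit the violation and radiotherapy exclusions to participants without a DLT. Analyse any retained DLT at the dose actually received.
- Reconcile this with the two-dose condition in Section 4.1.2 and Table 7, which would otherwise still drop a participant who has a DLT after the first dose and never receives the second.
- Document each exclusion and its reason before the model update.
- For Part A, report every participant excluded under either rule with DLT status, and add a sensitivity estimate of the MTD if any had a DLT.

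The cost is wording and at most one re-run of the model. The downside is that a DLT partly due to a violation may be counted, which errs on the cautious side.
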